7.2.2 Secondary Efficacy Criteria

The secondary endpoint will be analysed as described in the CTP and above for the primary endpoint.

Trial ID: LP0084-1369	Date: 27-May-2018	Version: 1.0 Page 9 of 14
-----------------------	-------------------	------------------------------

7.3 Analysis of Safety

7.3.1 Adverse Events

AEs will be analysed as described in the CTP. AE tables will show the number of subjects and events. When counting the number of events multiple occurrences of the same preferred term within a subject will be counted as multiple events. Due to the premature stop of the trial no statistical testing will be performed for AEs. The CTP specified that serious adverse events (SAEs) occurring outside the treatment areas and considered not related to IMP in the main trials, should not be collected. Sporadically reported SAEs outside treatment area will therefore be removed from the ADaM datasets, but will appear in the SDTM datasets and the listing.

AEs that were ongoing at the end of the main trials were re-entered in the LP0084-1369 database for subjects enrolled in LP0084-1369, and these events were marked in the SDTM domain SUPPAE as such. A total of 69 AEs were re-entered in the LP0084-1369 database. The corresponding AEs in the main trials were identified by merging by subject, reported term and start date. In the 4 cases where the AEs in the main trials could not be identified by merging a manual review was performed to identify the corresponding AEs in the main trials. In cases of duplicate AEs only the AEs recorded in LP0084-1369 were included in the ADaM dataset. The analyses of AEs will be based on the actual treatment.

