8.1 Schedule of Trial Procedures

Table 1 Schedule of Trial Procedures

	Visit 1 ¹⁾	Visit 2	Visit 3	Visit 4	Visit 5	Unscheduled or Early Termination
Day / Month		Month 6 ²⁾	Month 12	Month 18	Month 24	N/A
Visit window	N/A	±16 days ²⁾	±16 days	±16 days	±16 days	N/A
Informed consent	X					
Inclusion/exclusion criteria	X					
Concomitant medication and procedures ³⁾		X	X	X	X	X
AE(s) ⁴⁾		X	X	X	X	X
Scarring		X	X	X	X	X
End of Trial					X	X ⁵⁾

1) Visit 1 ideally coincides with visit 11 (month 14) of the main trial and should be performed before or at Visit 2 of the present trial.
 2) Visit 2 is 6 months after visit 11 (month 14) of main trial and the visit window is relative to visit 11.
 3) Information regarding medication or treatments which may suppress the immune system in subjects or which may alter the course of AK or SCC. Also, any medications (topical or systemic) and procedures used for AEs in the treatment area.
 4) Within treatment area only (SAEs outside treatment area are only collected if deemed related to IMP in main trial or reported elsewhere in the CRF).
 5) Early termination only.

All assessments in this trial will be made in the treatment area that was documented in the main trial (LP0084-1193, -1194, -1195 and -1196). The study transparency used in the main trial should be used to reidentify the treatment area for assessment of the treated skin on the face, chest, or scalp for all visits in the present trial.

Trial ID: LP0084-1369	Date: 25-Jul-2017	Version: 2.0 Page 17 of 52
-----------------------	-------------------	-------------------------------

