8.4 Adverse Events

Only AEs in the treatment area (including keratoacanthoma [KA], SCC, or other skin neoplasia) will be collected. AEs must be assessed and recorded as specified in section [9](#).

If Visit 1 does not coincide with Visit 11 of the main trial (LP0084-1193, -1194, -1195 and -1196) events in the treatment area for the period between the two visits must be recorded at Visit 2.

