8.6 End of Trial

The End of Trial Form must be completed for all enrolled subjects. This includes last attended scheduled visit number and primary reason for withdrawal .

Trial ID: LP0084-1369	Date: 25-Jul-2017	Version: 2.0 Page 19 of 52
-----------------------	-------------------	-------------------------------

9 Adverse Events

- AEs and serious adverse events (SAEs) are defined in Appendix 3: Definitions of Adverse Events and serious Adverse Events.
- Classification of AEs in terms of severity, causality and outcome are defined in Appendix 4: Classification of Adverse Events.

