9.1 Collection of Adverse Events

In this extension protocol, where no treatment is being administered, all AEs and SAEs occurring in the area treated in the phase 3 trials (treatment area) will be routinely collected from completion of Visit 11 in the main trial until the subject's last visit to the clinic.

SAEs occurring outside the treatment area in the main trial, and considered not related to IMP in these trials, will not be systematically collected. For an overview of which AEs should be collected, see table below.

Table 2 Overview of AEs to be Collected

AE collection		
	Inside treatment area	Outside treatment area
AEs	All	None
SAEs	All	Related to IMP in main trials Referenced elsewhere in the CRF (e.g. death on end of trial form, hospitalisation as reason for missing visit)

AEs must be assessed by medically qualified personnel. A qualified experienced dermatologist must conduct all dermatologic examinations and AE evaluation of the treatment area defined in the main trials (LP0084-1193, -1194, -1195, -1196).

At all visits, the subject will be asked a non-leading question by the (sub)investigator about AEs, for example: "How have you felt since I saw you last?" No specific symptoms should be asked for. It is important that the (sub)investigator also observes the subject for any changes not reported by the subject and records these changes.

Trial ID: LP0084-1369	Date: 25-Jul-2017	Version: 2.0 Page 20 of 52
-----------------------	-------------------	-------------------------------

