11.3.6.1 Adverse Events

AEs will be coded during the course of the trial according to Medical Dictionary for Regulatory Activities (MedDRA). AEs will be presented by preferred terms and primary system organ class (SOC).

AEs from the 24-month trial period, will be summarised and included in the subject data listings by its start date. All adverse events will be considered treatment-emergent and will be included in the tabulations described in the following. In each of the tabulations, AEs are defined by MedDRA preferred terms within primary SOC.

An overall summary of the number (percentage) of subjects with any AEs, SAEs, premature discontinuations from the trial due to AEs, treatment-related AEs and severe AEs will be presented overall and by treatment group in main trial.

The number of subjects experiencing each type of AEs will be tabulated by treatment group in main trial regardless of the number of times each AE is reported by each subject. The percentage of subjects with any AEs will be compared between treatment groups by a chi-square test or Fisher's exact test (if expected cell count < 5).

Severity

The severity for each type of AE will be tabulated by treatment group in main trial. Where there are several recordings of severity for a given type of AE, severity will be taken as the most severe recording for that AE.

Causal relationship

The causal relationship to IMP for each type of AE will be tabulated by treatment group. Where there are several recordings of causal relationship to the IMP for a given type of AE, causal relationship will be taken as the most-related recording from the last report of that AE,

Trial ID: LP0084-1369	Date: 25-Jul-2017	Version: 2.0 Page 27 of 52
-----------------------	-------------------	-------------------------------

since that is when the (sub)investigator will be in possession of most information and so best able to judge causal relationship.

Related AEs are defined as AEs for which the (sub)investigator has not described the causal relationship to IMP as 'not related'. The number of subjects experiencing each type of related AE will be tabulated regardless of the number of times each related AE is reported by each subject. The percentage of subjects with related AEs will be compared between treatment groups by a chi-square test or Fisher's exact test (if expected cell count < 5).

Most common adverse events

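### SAP 7.3.1 misstates the protocol's rule on SAEs outside the treatment area, and the ADaM removal built on it can drop protocol-collected SAEs from the by-arm safety tables

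*SAP*

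**What the plan says.** SAP 7.3.1 makes two linked statements. It reports the protocol as having specified that SAEs outside the treatment areas and "considered not related to IMP in the main trials, should not be collected". It then concludes that "Sporadically reported SAEs outside treatment area will therefore be removed from the ADaM datasets", while keeping them in SDTM and in the listing. It does not define which reports count as sporadic, and it makes no exception.

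The protocol's rule is different:

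- Section 9.1 (text): outside-area SAEs "considered not related to IMP in these trials, will not be systematically collected". The reader is then sent to Table 2.
- Section 9.1, Table 2: two classes of outside-area SAE are collected. One is SAEs related to the product in the main trials. The other is "Referenced elsewhere in the CRF (e.g. death on end of trial form, hospitalisation as reason for missing visit").
- Section 8.1, Table 1, footnote 4: "SAEs outside treatment area are only collected if deemed related to IMP in main trial or reported elsewhere in the CRF".
- Section 8.4, a general sentence: "Only AEs in the treatment area (including keratoacanthoma [KA], SCC, or other skin neoplasia) will be collected".

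On analysis, protocol 11.3.6.1 says: "All adverse events will be considered treatment-emergent and will be included in the tabulations described in the following". SAP 7.3.1 itself opens by adopting the protocol's AE analysis.

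**The concern.** The SAP drops the qualifier about systematic collection and leaves out the whole second class of Table 2. It then uses the shortened rule as its reason for a data-handling step. A programmer following SAP 7.3.1 would have grounds to delete from ADaM an unrelated fatal or hospitalised outside-area SAE that the protocol asked sites to report.

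What is at stake is the by-arm count of serious events. A listing or a narrative shows that an event happened, but it does not give the comparison of ingenol disoxate with vehicle that the tables are meant to give. Deaths would still be visible by arm as a reason for leaving the trial. A non-fatal hospitalisation that only caused a missed visit would appear in no by-arm AE table.

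Protocol 11.3.8 allows changes to the planned analysis if they are described and justified. Here the change is described, but the justification given is a rule that the protocol does not contain.

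**Working it through.** There is no sample size, power or alpha figure to reproduce on this point. The check compares the two rules and then counts the tables affected.

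**Step 1: the two rules, for an SAE outside the treatment area**

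- Related to the product in the main trials. Protocol: collected. SAP premise: not mentioned.
- Unrelated, but mentioned elsewhere in the CRF. Protocol: collected. SAP premise: not to be collected.
- Unrelated, and not mentioned elsewhere. Protocol: not systematically collected. SAP premise: not to be collected.

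The second row is the conflict. The class is not a marginal one in the protocol: one of its named sources is the End of Trial form, and section 8.6 says "The End of Trial Form must be completed for all enrolled subjects".

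**Step 2: the AE tables in SAP Appendix I**

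There are 12 AE table types, each produced for the enrolled subjects (n = 562, SAP 6.1) and for the follow-up analysis set, FUAS (n = 1172, SAP 6.4): 12 × 2 = 24 tables. For an unrelated outside-area SAE mentioned elsewhere in the CRF:

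- Always affected: AE summary, AEs by SOC and preferred term, AEs by severity, SAEs by SOC and preferred term, SAEs by causal relationship. That is 5 types × 2 sets = 10 tables.
- Affected only in some cases: frequent AEs (if the term reaches 2% in the active group) and AEs leading to withdrawal (if the event led to withdrawal). That is 2 × 2 = 4, so up to 14 tables.
- Affected only if product-related SAEs were removed as well: related AEs, and related AEs by severity. That is 2 × 2 = 4, so up to 18 tables.
- Never affected: the two neoplasia types confined to the treatment area, and non-serious AEs. That is 3 × 2 = 6.

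Check: 10 + 4 + 4 + 6 = 24.

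**Step 3: what the count means**

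The ten tables are five presentations shown twice. An enrolled subject must have been treated and evaluated at Visit 11 of a main trial, so an extension event falls in both the enrolled set and the FUAS. Extension SAEs can arise only in the 562 enrolled subjects, and the larger FUAS denominator adds no further extension events. The documents do not say how many outside-area SAEs were reported, so no rate or arm difference can be computed.

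**The case against.** The strongest reply is that a sporadic report can naturally mean one made outside the collection rule. On that reading the two Table 2 classes were never meant to be removed, and the opening reference to the protocol's AE analysis supports it. The reading is possible, but the SAP does not state it. The stated premise covers every unrelated outside-area SAE, and the word linking premise to removal carries that scope forward. If the narrower meaning was intended, one sentence would settle it.

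Second, protocol 8.4 says that only treatment-area AEs are collected, so the protocol is not uniform, and the 11.3.6.1 sentence on including all AEs does not address location. Both observations are fair. However, the SAP relies on the specific rule for outside-area SAEs, which Table 1 footnote 4 and Table 2 spell out and which qualifies the general sentence.

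Third, little is lost. The events stay in SDTM and the SAE listing, protocol 11.3.6.1 requires a narrative for each SAE, and disposition shows deaths by arm. The SAP drops AE testing. Capture outside the area is selective, so by-arm counts are hard to interpret. All of this stands and limits the harm, but none of it supplies the missing counts.

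A reader might also infer that product-related outside-area SAEs are removed, because the removal sentence is not worded as limited to unrelated ones. The premise concerns unrelated SAEs only, so this is an ambiguity and not a finding.

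**Conclusion.** The point holds as a misstated rule with a limited consequence. SAP 7.3.1 attributes to the protocol a position that Table 1 footnote 4 and Table 2 contradict. On its most direct reading, any protocol-collected, unrelated outside-area SAE would be absent from five AE table types, each shown for two sets. This rests on two assumptions: that at least one such SAE was reported, and that the removal is applied to the full scope of the stated premise.

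A reader might infer that serious events are suppressed, or that ten tables are known to be wrong. The documents support neither. The number of events may be zero, and any that exist remain in SDTM, the listing and the narratives. The SCC and skin neoplasia endpoints are confined to the treatment area and do not change.

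The correction should be made, but it bears on the completeness of the safety tables and not on the trial's main comparison.

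**What to change.** In SAP 7.3.1:

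1. Restate both Table 2 classes of outside-area SAE and cite Table 2 as the rule applied.
2. Limit removal from ADaM to outside-area SAEs that fall in neither class. This also settles the ambiguity about product-related SAEs.
3. Keep both collected classes in ADaM with a location flag, and count them in the planned by-arm AE and SAE tables, consistent with protocol 11.3.6.1.
4. Show the outside-area events as an identifiable subset, with a footnote that collection outside the area was selective during the extension.

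Moving these events to a separate block and labelling the main tables as treatment-area only would not do. It would still leave the events out of the planned tables. The label could also be false for the FUAS tables, which include main-trial data from week 8 to month 14: the documents do not say that AE collection in the main trials was confined to the treatment area.

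If the sponsor prefers to exclude these events, it should justify that as a departure from the protocol and not attribute it to the protocol.

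The cost is a few SAP sentences, one flag, a subset display and a footnote. The SAP does not say whether reasons for missed visits, or a link to the other CRF page, are held in SDTM. Matching SAEs to End of Trial and missed-visit records may therefore need manual review. The resulting counts are descriptive only.

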7.3.2 Scarring

Scarring will be presented in shift tables for the safety analysis set as well as for the set of subjects enrolled into trial LP0084-1369. All data on scarring collected in the 4 main trials and in trial LP0084-1369 will be included in the shift tables. The analyses of scarring will be based on the actual treatment.

7.3.3 Concomitant medication

Concomitant medication will be tabulated by ATC4 code and WHO dictionary derived term for subjects enrolled into trial LP0084-1369. Only concomitant medications registered in trial LP0084-1369 will be included. The analyses of concomitant medication will be based on the actual treatment.

Trial ID: LP0084-1369	Date: 27-May-2018	Version: 1.0 Page 10 of 14
-----------------------	-------------------	-------------------------------

7.4 General Principles

7.4.1 Handling of Drop-outs and Missing Values

Relatively few subjects in the FAS are expected to experience an event of SCC or other skin neoplasia, and therefore the amount of censoring in the analyses of the primary and secondary endpoints is expected to be substantial. All subjects who completed the 4 main trials without a prior event of SCC or other skin neoplasia and choose not to participate in the extension trial will be censored at the time they complete the main trial. All discontinued subjects without a prior event of SCC or other skin neoplasia will be censored at the time of discontinuation from the trial. The survival analyses performed will be evaluated in the presence of censoring.

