11.3.3 Exposure and Treatment Compliance

11.3.4 Analysis of Primary Endpoint

The null hypothesis is that there is no difference in time to first SCC between ingenol disoxate gel and vehicle gel. The hypothesis will be tested against the two-sided alternative that there is a difference between the two treatment groups.

Primary endpoint is time to first SCC in the treatment area from Visit 2 in trials LP0084-1193, -1194, -1195 and -1196.

Only the SCC confirmed by the IAC will be used in the primary endpoint analysis.

The annual and the 3-year and 2 months cumulative incidence of first event of SCC will be calculated for each treatment group (active and vehicle) in main trial using methods of survival analysis in the presence of censoring. The cumulative incidence rates will be presented by treatment group for the event of first SCC as primary endpoint. A proportional hazards model will be fitted if the model assumptions are valid. Log-rank test comparing the two treatment groups will be performed. For descriptive purposes, as an additional analysis, the difference in cumulative incidence rates between the two arms will be estimated and presented together with its 95% confidence interval. A landmark analysis will additionally be performed in order to exclude SCC and other neoplasia reported within the first 8 weeks which are not assumed to be associated with the trial treatment. This corresponds to left-truncation of the trial period at 8 weeks, the analysis will otherwise be conducted as above. Patients who experience a SCC before the 8-week landmark time point are excluded from the landmark analysis.

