11.3.9 Handling of Missing Values

Missing values for time to occurrence of SCC or other neoplasia will be handled as censored observations.

12 Trial Committees

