7.2.1 Primary Efficacy Criterion

The primary endpoint will be analysed as described in the clinical trial protocol (CTP).

The proportional hazards model will include planned treatment as explanatory variable, and have the proportional hazards assumptions checked by assessing whether or not the survival functions cross each other. The hazard ratio and corresponding 95% Wald confidence limits will be estimated within the proportional hazards model with planned treatment group as explanatory variable. A likelihood ratio test within the proportional hazards model will be applied for comparison of treatment groups. The results will be presented by treatment location (face/chest or scalp) and treatment group within treatment location as well as overall by treatment group (ingenol disoxate versus vehicle). The analysis will be based on the FAS.

The cumulative incidence rate will be calculated as the number of subjects with one or more events divided by the total observation period across all subjects in the FAS. The lower and upper limits of the 95% confidence interval will be calculated using the following SAS code:

Lower=((cinv(0.025,#subjects*2)/2)/total_obs_period)

Upper = ((cinv(0.975,2*(#subjects+1))/2)/total_obs_period)

The cumulative incidence rate and corresponding 95% confidence interval will also be presented by treatment location (face/chest or scalp) and treatment group within treatment location as well as overall by treatment group (ingenol disoxate versus vehicle).

For the landmark analysis described in the CTP time=0 will be defined as the date of visit 7 (week 8). This analysis will be based on the follow-up analysis set (FUAS) excluding subjects who experience an event prior to visit 7. Subjects in FUAS who do not have a visit 7, will have the date of their visit 7 imputed as the date of their visit 6 (week 4) plus 28 days.

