- Kaplan-Meier curve for SCC (scalp): full analysis set
- Kaplan-Meier curve for SCC (landmark analysis, scalp): follow-up analysis set
- Kaplan-Meier curve for SCC: full analysis set
- Kaplan-Meier curve for SCC (landmark analysis): follow-up analysis set
- Kaplan-Meier curve for SCC or other skin neoplasia (face/chest): full analysis set
- Kaplan-Meier curve for SCC or other skin neoplasia (landmark analysis, face/chest): follow-up analysis set
- Kaplan-Meier curve for SCC or other skin neoplasia (scalp): full analysis set
- Kaplan-Meier curve for SCC or other skin neoplasia (landmark analysis, scalp): full analysis set

Trial ID: LP0084-1369	Date: 27-May-2018	Version: 1.0 Page 14 of 14
------------------------------	--------------------------	-------------------------------

- Kaplan-Meier curve for SCC or other skin neoplasia: full analysis set
- Kaplan-Meier curve for SCC or other skin neoplasia (landmark analysis): follow-up analysis set
- Onset of each SCC for face/chest (left panel) and scalp (right panel): follow-up analysis set
- Onset of each SCC or other skin neoplasia for face/chest (left panel) and scalp (right panel): follow-up analysis set

Listings

- Serious adverse events (week 8 - months 14 in main trials and LP0084-1369): follow-up analysis set

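### The protocol's survival-based cumulative incidence of SCC censors deaths, so read as one minus Kaplan-Meier it slightly overstates the proportion of subjects who develop SCC

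*SAP*

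**What the plan says.** Protocol 11.3.4 plans the annual and the 3-year-2-month cumulative incidence of first SCC in each arm "using methods of survival analysis in the presence of censoring". It adds, as a descriptive analysis, the difference between arms with a 95% confidence interval. For the comparison it says "Log-rank test comparing the two treatment groups will be performed", with a proportional hazards model if its assumptions hold. Protocol 11.3.5 applies the same analysis to SCC or other skin neoplasia.

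SAP 7.2.1 carries the protocol analysis over by reference. It also defines one quantity by formula, taken over the full analysis set and given a chi-square-based interval: "The cumulative incidence rate will be calculated as the number of subjects with one or more events divided by the total observation period across all" …

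SAP Appendix I lists figures such as "Kaplan-Meier curve for SCC: full analysis set".

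On censoring, Protocol 11.3.9 says "Missing values for time to occurrence of SCC or other neoplasia will be handled as censored observations", and SAP 7.4.1 says "All discontinued subjects without a prior event of SCC or other skin neoplasia will be censored at the time of discontinuation from the trial". Protocol 7.7 includes death among the reasons for withdrawal and makes no exception for it. Table 2 in Protocol 9.1 shows that deaths are captured, giving as an example "death on end of trial form, hospitalisation as reason for missing visit". Neither document mentions death as a competing event.

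**The concern.** A dropout can still develop SCC after leaving, so censoring is a reasonable way to treat that subject. A subject who has died cannot. Kaplan-Meier spreads the future SCC risk of every censored subject over those still under observation. When deaths are among the censored, one minus Kaplan-Meier estimates the SCC risk in a population where nobody dies. That is higher than the proportion of treated subjects who go on to have an SCC.

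At stake are the absolute risks that Protocol 11.3.4 promises for each arm, the descriptive arm difference, and the risk that a reader takes from the Kaplan-Meier figures. Absolute SCC risk after treatment is a main reason for the trial (Protocol 3.3), so the plan should say which risk it reports.

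**Working it through.** **Inputs from the documents**
- Assumed 38-month SCC rates of 4.0% and 6.0%, with 800 active and 400 vehicle subjects (Protocol 11.1).
- Follow-up T = 38/12 = 3.167 years (Protocol 3.3).
- Full analysis set of 1234, of whom at most 562 entered the extension (SAP 6.1, 6.2); early stop (SAP 5).

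**Assumed.** Mortality is not in the documents. A constant death hazard m of 1–4% per year is used in both arms, with a constant SCC hazard h.

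**1. The plan's own precision figures.** The upper limit p + 1.96·√(p(1−p)/n) gives:
- p = 4.0%: 5.36% (n = 800) and 5.92% (n = 400)
- p = 6.0%: 7.65% (n = 800) and 8.33% (n = 400)

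All four match Protocol 11.1. The distance from estimate to upper limit is 1.36 to 2.33 percentage points.

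**2. Cumulative incidence with death censored and with death competing.** Let F be the value of one minus Kaplan-Meier at 38 months.
- h = −ln(1−F)/T, which is 0.01289 per year for 4% and 0.01954 for 6%.
- One minus Kaplan-Meier at time t: 1 − exp(−ht).
- Death as a competing event: h/(h+m) × [1 − exp(−(h+m)t)].

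Example, F = 4%, m = 4%, t = 3.167: 0.01289/0.05289 × [1 − exp(−0.1675)] = 0.2437 × 0.1542 = 3.76%.

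| Deaths per year | 4.00% at 38 months becomes | 6.00% at 38 months becomes | Relative excess |
|---|---|---|---|
| 1% | 3.94% | 5.91% | 1.6% |
| 2% | 3.88% | 5.82% | 3.2% |
| 3% | 3.82% | 5.73% | 4.8% |
| 4% | 3.76% | 5.64% | 6.4% |

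The excess at 38 months is 0.06 to 0.36 points. A simulation with n = 800, F = 4% and m = 2% (3000 runs) gave 4.01% for one minus Kaplan-Meier and 3.89% with death competing, in agreement with the 2% row.

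**3. The same at 14 months.** With the same hazards, one minus Kaplan-Meier is 1.49% (4% scenario) or 2.25% (6% scenario). With death competing these become 1.48–1.46% and 2.24–2.20%. The excess is about 0.01 to 0.05 points. This horizon matters because 1234 − 562 = 672 subjects (54%) never entered the extension and have no follow-up beyond about month 14.

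**4. The person-time rate in SAP 7.2.1.** Expected events are h/(h+m) × [1 − exp(−(h+m)T)]. Expected person-time per subject is [1 − exp(−(h+m)T)]/(h+m). The ratio is h whatever m is: 1.29 per 100 person-years in the 4% scenario and 1.95 in the 6% scenario. The simulation gave 1.294 against a true 1.289.

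**5. The arm difference.** With equal mortality in both arms, a 6.00% v 4.00% difference of 2.00 points becomes 1.97 (m = 1%) to 1.88 (m = 4%). Equal SCC hazards and equal mortality give a difference of zero under either estimator.

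**The case against.** The strongest objection is that the plan's incidence figure is not a Kaplan-Meier quantity at all. The only incidence that the SAP defines by formula is events divided by observation time. A subject who dies stops adding time, so the dead are not carried as still at risk. Appendix I lists incidence tables and Kaplan-Meier figures, but no table explicitly of annual or 38-month risks from one minus Kaplan-Meier. This stands. A reader might infer from the censoring rule that every reported SCC incidence is too high. The SAP formula does not support that, and step 4 shows why. The fault in that formula is its name: it is called a cumulative incidence rate but is an incidence rate.

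A reader might also infer that the treatment comparison is biased. It is not. The log-rank test and the Cox model compare cause-specific hazards, and censoring at death is standard for them. With similar mortality in the arms, a null difference in cumulative incidence stays null and a real one shrinks only slightly. The plan itself calls that difference descriptive.

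Third, the risk without death and the risk in its presence are both legitimate targets, and the protocol does not say which it means. That is fair. It also means the choice should be stated, because the name suggests the proportion affected and the censoring rule delivers something else.

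Fourth, the 38-month figures are an upper bound on the effect. The trial stopped early. If the first visit fell in Q2 2017 as planned (Protocol 6.2), month 38 would lie after the SAP date of 27 May 2018, even with the longest gap between Visit 11 and Visit 1 that Protocol 8.1 allows (about 6.5 months). This also stands.

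Finally, deaths by arm are largely covered already: Protocol 11.3.1 presents reasons for leaving by treatment group, and Appendix I lists disposition tables.

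**Conclusion.** The point holds for the protocol's survival-based cumulative incidence, for the arm difference built on it, and for risks read from the Kaplan-Meier figures, for both the primary and the secondary endpoint. It does not extend to the SAP's person-time rate, the log-rank test or the hazard ratio.

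The size is small. At an assumed mortality of 1–4% per year, the excess is 0.06–0.36 points at 38 months and about 0.01–0.05 points at 14 months, against 1.36–2.33 points from estimate to upper confidence limit in the plan. The result rests on three assumptions: that the protocol's wording means one minus Kaplan-Meier, which is the natural reading but is not stated; that hazards are constant; and that mortality lies in the range shown. The direction of the bias depends only on the first. It is a minor improvement, worth making because it is in one direction and nearly free to remove.

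**What to change.** In SAP 7.2.1 and 7.4.1:

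- State that death before the first event is a competing event in the cumulative incidence. Estimate the cumulative incidence at each reported time, and the arm difference with its 95% confidence interval, by the Aalen-Johansen method. Do the same for the secondary endpoint.
- Keep the log-rank test and the Cox model with deaths censored, and describe them as cause-specific.
- Call the events-per-person-time quantity an incidence rate, with its unit, so that it is not confused with the cumulative incidence.

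The cost is a few sentences in the SAP and slightly more analysis work. Death dates are needed from the main-trial data as well as from the extension. In the extension, the End of Trial form records the reason for withdrawal (Protocol 8.6). How the main trials recorded deaths is not in these documents and should be confirmed first.
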